### ***Atypical ductal hyperplasia (ADH) is a model of active surveillance for breast conditions.***

Since over 97% of women receive treatment for their disease immediately upon diagnosis, it has been difficult to evaluate the outcomes of an AS strategy for DCIS. However, there are other analogous clinical scenarios in which women are identified to be at increased risk for breast cancer, and are routinely offered close surveillance. One such example is atypical ductal hyperplasia (ADH) which, much like DCIS, is often diagnosed on a biopsy performed for a mammographic abnormality. ADH is found in approximately 10% of all benign breast biopsies, and is associated with the highest future risk of breast cancer among all benign diagnoses. It shares many histologic features with low grade DCIS for which it is often mistaken, even by specialized breast pathologists. The lifetime cumulative risk of invasive cancer among women with ADH has been reported to approach 15% at 25 years (Figure 1a), equivalent to approximately half the risk for invasive cancer in women not recognized to have DCIS and who were thus managed with biopsy alone (Figure 1b). The treatment recommendation for women with ADH is not surgery or radiation but rather close or active surveillance, usually with the option of endocrine therapy such as tamoxifen to reduce risk of subsequent invasive cancer.

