## **2.2 Hypothesis and Specific Aims:**

We hypothesize that there are differences in patient-centered clinical outcomes and Patient Reported Outcomes (PROs) between women who choose GCC versus AS, and that these differences can be compared using advanced analytic methods to allow for the expected treatment selection biases between groups.

The specific aims of this study are the following:

**Aim 1. Compare patient-reported outcomes (PROs) between patients diagnosed with ductal carcinoma in situ (DCIS) who received GCC to patients diagnosed with DCIS who underwent AS as well as those diagnosed with atypical ductal hyperplasia (ADH), and lobular carcinoma in situ LCIS/atypical lobular hyperplasia (ALH) (as proxies for DCIS active surveillance (AS) group) in a cross-sectional patient cohort at 6 selected study sites.**

PROs will be collected from surveys administered to patients diagnosed for either DCIS, ADH, LCIS, or ALH between January 1, 2012 and June 30, 2017 at each of six study sites: Duke University Medical Center (DUMC), Dana-Farber Cancer Institute (DFCI), MD Anderson Cancer Center (MDACC), Massachusetts General Hospital (MGH), Newton Wellesley Hospital (NWH), and Dana-Farber/Brigham and Women's Cancer Center (DF/BWCC) in clinical affiliation with South Shore Hospital (DFCI @ SSH). We are planning for survey data collection to begin in September 2017, but will officially commence upon IRB approval at each recruiting site. MDACC received their site's IRB approval on December 6, 2017 and has now been added to the DFCI IRB as a site. MDACC will now complete applicable study procedures as outlined in this protocol. DUMC received their site's IRB approval on February 27, 2018 and has now been added to the DFCI IRB as a site. Duke will now complete study procedures as outlined in this protocol. MGH has been added to the DFCI IRB as a site. MGH will now complete study procedures as outlined in this protocol. DFCI @ SSH has been added to the DFCI IRB as a site. DFCI @ SSH will now complete study procedures as outlined in this protocol. The DFCI study team will complete all patient recruitment steps for DFCI @ SSH. NWH has been added to the DFCI IRB as a site. NWH will now complete study procedures as outlined in this protocol.

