**Knowledge:** Among patients with DCIS only, DCIS and breast cancer knowledge will be measured with items adapted from the Breast Cancer Surgery Decision Quality Instrument (BCS-DQI), an instrument designed to evaluate the quality of breast cancer treatment decisions. A series of true/false questions used in a prior survey of women with DCIS will also be used to assess knowledge of facts specific to a DCIS diagnosis and treatment; items will be adapted for patients with an ADH/LCIS/ALH diagnosis.

**Decision-making:** Treatment goals and preferences will be assessed with the BCS-DQI which includes items designed to measure individual patient goals and concerns. Four items (The SURE scale) adapted from the Decisional Conflict Scale will be used to measure patients' uncertainty about which treatment and factors contributing to uncertainty. The 5 item Decision Regret Scale will be used to measure decisional regret. Patient perception of the decision process will be assessed using an adapted version of the Control Preferences Scale. Communication with physicians and sources of information about DCIS/ADH/LCIS/ALH management options will be assessed using items from a prior study of surgical decision-making.

**Risk perceptions:** We will assess risk perceptions in women with DCIS, LCIS/ALH or ADH using questions developed by Lerman and Croyle that have previously been used to measure risk perceptions in women with DCIS. This will ultimately be compared to actual risk of their condition based on published data.

**Quality of Life (QOL):** We will use the SF-12 to measure health-related QOL. A modified 19-item version of the Breast Cancer Prevention Trial (BCPT) Symptom Checklist will be used to evaluate commonly reported menopausal symptoms. The Breast-Q, a validated instrument to evaluate outcomes following surgery, will be used to evaluate satisfaction with appearance, self-image, and sexuality. Four items from the Quality of Life in Adult Cancer Survivors (QLACS) will be adapted to evaluate frequency (1=never; 7=always) of worries about DCIS, including concerns about future breast events and death from DCIS.

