6.2 Sample size and statistical power

Importantly, published data indicate that patients undergoing lumpectomy with radiation report comparable levels of pain and sensory disturbances as those undergoing mastectomy.⁵⁶ Thus, these treatment groups will be grouped together in the initial analysis, then a stratified analysis will be performed. Preliminary data among 582 women undergoing either lumpectomy or mastectomy indicate that the mean persistent pain intensity after breast surgery is 2.61 (DS 4.24).⁵⁵ Given a sample size of 900 patients in the GCC group and 300 in the AS group, we will be able to detect with 90% power at a level of 0.05 (2-sided) a difference in pain intensity score of 2 (from 2.61 to 0.61), which has been deemed to be a clinically meaningful difference.

Based upon the number of unique cases diagnosed with DCIS at each site between 2010 and 2013, we estimate that at all 6 study sites combined, approximately 1500 women will have been diagnosed with DCIS between January 1, 2012 and June 30, 2017 and will be eligible to participate. Our response rate in prior survey studies has been approximately 60% using the approach we will adapt to the current study; thus, we anticipate that about 900 women with DCIS will be accrued and will complete the survey across all study sites. These patients will be matched 3:1 to participants diagnosed with ADH or LCIS/ALH undergoing active surveillance. DCIS participants will be matched 3:1 to ADH/LCIS/ALH participants, based on matching criteria of age within 5 years, year of diagnosis, and study site. Additional matching criteria such as race, income, highest education level attained, and family history of breast cancer will be considered based upon stakeholder input during the protocol preparation process.

6.3 Analysis Plan: General Approach.

We will conduct descriptive analyses to profile the samples, including examination of proportions, means, and medians, as well as estimates of variability such as standard errors, ranges, and confidence intervals. We will identify outlying observations. Continuous data distributions will be evaluated for appropriateness of scale, and normal score transformations will be used where

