appropriate. Appropriate summary statistics, histograms, scatter plots, or one- or two-way contingency tables for women of each ethnic group will be computed. These analyses will be followed by bivariate analyses to examine the pairwise relationships among variables under examination. Demographic data will be compared for the respondents and non-respondents using chi-square or t-tests to assess selection bias. In addition to baseline disease and socio-demographic data, information relating to other treatment (e.g., endocrine treatment, radiation) as well as comorbidities will be collected, allowing us to control for potential confounding by these factors. We will also analyze the decision-making, DCIS knowledge, and risk perception data at baseline and compare these domains between the GCC and ADH/LCIS/ALH/AS groups. We will also systematically collect and evaluate and report on the upstaging rates and associated details from initial diagnosis of DCIS.

6.4 Management of missing data: As with all studies there is a risk of biased statistical inference with missing data and we will adhere closely to standards put forth by the National Research Council.⁷⁷ We will include details about missing patient data in all tables in subsequent analyses, and include a comparison of baseline characteristics of patients with and without missing data. We will carefully consider whether data missingness is random or whether missingness may be attributable to a certain factor and therefore not random (e.g., older women may be less likely to answer questions). We will assess non-response bias by comparing available characteristics in both patients and providers (e.g., practice type) among responders and non-responders.

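### SAP 6.3 compares decision-making between GCC and a pooled AS group that is about nine-tenths ADH/ALH/LCIS women, whose decision was not GCC versus AS for DCIS

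*SAP*

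**What the plan says.** SAP section 6.3, repeated in protocol section 6.3, plans to analyse decision-making, DCIS knowledge and risk perception and to "compare these domains between the GCC and ADH/LCIS/ALH/AS groups". This point is about decision-making only.

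The hypothesis in protocol section 2.2 is framed as a difference "between women who choose GCC versus AS". The same section lists decision quality among the patient-reported measures for weighing GCC against AS.

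Protocol section 5.2 describes the decision instruments:

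- Goals: "Treatment goals and preferences will be assessed with the BCS-DQI which includes items designed to measure individual patient goals and concerns". The BCS-DQI is the Breast Cancer Surgery Decision Quality Instrument.
- Conflict: the SURE items address patients' "uncertainty about which treatment and factors contributing to uncertainty".
- Regret: the five-item Decision Regret Scale.
- Process: an adapted Control Preferences Scale, and communication items drawn from a surgical decision study and applied to all four diagnoses.

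Protocol section 3.0 explains the comparator. Too few women with DCIS are on AS (2-3%), so women with ADH, ALH or LCIS, whose routine recommendation is surveillance, are added as proxies. The reason given is that these lesions are managed by follow-up and surveillance. The sizing in section 6.2 reads "Given a sample size of 900 patients in the GCC group and 300 in the AS group". Section 4.0 counts the 300 as LCIS, ADH or ALH cases, whereas section 5.5.1 lets women with DCIS who chose AS sit among the comparators and says they will be sought out individually.

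**The concern.** The proxy argument in section 3.0 is about how the women are managed. It supports comparing what life under surveillance is like: pain, symptoms, quality of life. It does not obviously carry over to scores about making a decision. A woman with DCIS who goes on AS departs from what over 97% of such women receive, while a woman with ADH, ALH or LCIS on surveillance follows the routine recommendation. Both can answer items on goals, conflict and regret, but they are rating different decisions.

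If the two are pooled, the result carries the label GCC versus AS but is almost wholly determined by women who were not choosing between those options for DCIS. Matching on age, year of diagnosis and site, or adjusting for treatment and comorbidity, does not help, because the scores refer to different decisions. At stake is one of the domains the protocol offers patients and clinicians for weighing the two strategies.

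**Working it through.** **Inputs.** Eligible pool: "approximately 1500 women will have been diagnosed with DCIS" (SAP 6.2). Response: 60% (SAP 6.2). Share of women with DCIS offered and/or undergoing AS: 2-3% (protocol 3.0). AS group: 300 (SAP 6.2).

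**Reproducing the plan's figure.** 1500 x 0.60 = 900, and 900/300 gives the 3:1 ratio. Both agree with the plan. The documents give no figure for the make-up of the AS group, so it is derived here.

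**Women with DCIS on AS.** a = 1500 x AS share x response. At 2%: 1500 x 0.02 x 0.60 = 18. At 3%: 1500 x 0.03 x 0.60 = 27.

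**Proxy share.** The documents leave open whether these women count inside the 300 or are added to it. Inside: (300 - a)/300. Added: 300/(300 + a).

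| AS share | Response of AS women | a | Proxy share, inside 300 | Proxy share, added to 300 |
|---|---|---|---|---|
| 2% | 60% | 18 | 94.0% | 94.3% |
| 3% | 60% | 27 | 91.0% | 91.7% |
| 2% | 100% (assumed) | 30 | 90.0% | 90.9% |
| 3% | 80% (assumed) | 36 | 88.0% | 89.3% |
| 3% | 100% (assumed) | 45 | 85.0% | 87.0% |

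The assumed rows allow for section 5.5.1's promise to seek these women out. If the 300 are all ADH/ALH/LCIS, as in section 4.0, and no woman with DCIS on AS is added, the share is 100%. At the other extreme, the treatments listed in protocol section 1.2 sum to 23.8 + 43 + 26.5 = 93.3%. Counting the whole remaining 6.7% as AS, against that section's own figure of 97% treated, gives a = 60.3 and a proxy share of 80-83%.

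**What pooling does.** The pooled AS mean is w x (mean of DCIS on AS) + (1 - w) x (proxy mean), with w between 18/318 = 5.7% and 27/300 = 9.0%. Suppose women with DCIS on AS differed from GCC by 1 SD and the proxies did not differ at all. The pooled contrast would then show only about 0.06 to 0.09 SD.

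**Precision of the two contrasts** (95% half-width in SD units, ignoring matching):

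- Within DCIS, 18 v 882: 1.96 x sqrt(1/18 + 1/882) = 0.47.
- Within DCIS, 27 v 873: 1.96 x sqrt(1/27 + 1/873) = 0.38.
- Pooled, 300 v 900: 1.96 x sqrt(1/300 + 1/900) = 0.13.

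With 18 to 27 women on AS, the within-DCIS difference detectable with 90% power (two-sided 0.05) is about 0.77 to 0.63 SD. The pooled interval is about a third as wide, but it is centred on a different quantity.

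**The case against.** The strongest reply is that the proxy design is disclosed and deliberate. Section 3.0 says that women with DCIS on AS are too few to compare with GCC, and Aim 1 defines the comparator to include the proxies. That is so, and it is why a within-DCIS contrast can only be descriptive. But the stated rationale is shared management, and no section extends it to decision outcomes.

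Other objections stand and limit the point:

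- A reader might infer that the proxies had no decision to rate. The documents do not support that. The sentence "The treatment recommendation for women with ADH is not surgery or radiation but rather close or active surveillance" is about ADH alone. Section 3.0 extends the surveillance recommendation to ALH and LCIS, but not the exclusion of surgery. Section 1.2 describes endocrine options and reports 56 bilateral prophylactic mastectomies in an LCIS series of 1060 women.
- A reader might infer that restricting to DCIS gives a clean comparison of choosers. It does not. Section 3.0 speaks of 2-3% being offered and/or undergoing AS, so many GCC women may never have been offered it.
- A reader might infer that surgical items go unadapted to the proxies. Section 5.2 states adaptation for that group only for the knowledge items, but the survey is not in the text available. Section 5.5.1 mentions skip patterns, and the communication items cover all four diagnoses. Adaptation cannot be judged either way.
- A reader might infer that pooling will make AS look the easier or less regretted choice. That is plausible, but no score or effect in the documents establishes a direction.

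**Conclusion.** The concern holds in a limited form. As written, the decision-making comparison in SAP 6.3 is dominated by women whose decision was not GCC versus AS for DCIS. They are about 91-94% of the AS group at 2-3% AS and 60% response, and at least 85% at 3% AS with full response. A flat claim of over 90% would go beyond the documents, because the figure depends on the response achieved among women with DCIS on AS. The conclusion needs only that these women remain a small minority, which is so in every case tabulated.

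The proxies' scores may be valid for their own decisions. The pooled contrast nevertheless does not inform the hypothesis on decision quality, and the sign and size of any bias are unknown. The main focus on pain and physical symptoms is untouched. This is a cheap improvement to a secondary domain, not a fault in the main comparison.

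**What to change.** In SAP section 6.3:

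- Report decision goals, SURE and Decision Regret in three separate groups: GCC, DCIS on AS, and ADH/ALH/LCIS. State which decision each group is rating.
- Give the within-DCIS contrast of GCC with AS as a descriptive estimate with a 95% confidence interval, and say beside it that many GCC women may not have been offered AS.
- Draw no inference about deciding between GCC and AS from the ADH/ALH/LCIS scores.
- Keep the pooled proxy comparison for pain, symptoms and quality of life.

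This changes wording only and uses data already planned for collection. The price is precision: the decision contrast for AS in DCIS would rest on roughly 18 to 27 women and could not settle moderate differences.
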